6.1.2. Missing Data Handling

No imputation of missing data will be performed unless otherwise specified.

The following rules will be used to impute partial dates for AE or concomitant medications:

- Partial start dates:
 - If only the day of the month is missing:
The onset date will be set to the first day of the month unless the month is the same as the first dose, where the onset date will be set to the date of the first dose date. However, if this

- imputation leads to an onset date later than the end date of the event, the start date will still be set as the first day of the month.
- If both the day and month are missing:
The day and month will be assumed to be January 1 of the year, unless the event occurred in the same year as the first dose, where the start date will be set to the day of the first dose. However, if this imputation leads to an onset date later than the end date of the event, the start date will still be set as January 1 of the year.
- If the start date is completely missing:
The missing start date will be set to the date of the first dose. However, if this imputation leads to an onset date later than the end date of the event, the start date will be set to the first day of the month/year of the end date.

- Partial end dates:
 - If only the day is missing: the end date will be set to the last day of the month or the last follow-up date whichever earlier.
 - If both the day and the month are missing: the end date will be set to December 31 or the last follow-up date whichever earlier.
 - If the end date is completely missing: no imputation will be implemented.

6.2. Analysis Populations

The study populations to be used in the analyses are defined as follows:

Intent-to-Treat (ITT) Population: All ibrexafungerp-treated subjects.

Modified Intent-to-Treat (MITT) Population: All treated subjects who have a positive culture for *Candida* species at Screening.

Per-Protocol (PP) Population: All MITT subjects who have completed the study drug treatment, who did not have major protocol deviations likely to affect study efficacy AND who have a TOC evaluation.

Safety Population: All enrolled subjects who received at least one dose of study drug.

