11.4. Early Termination

If the subject experiences persistence or worsening or recurrence of symptoms that per the investigator's assessment (e.g., symptoms ≥ 4) warrant the use of additional antifungal therapy, and the investigator does not consider continuing treatment with ibrexafungerp for a Second Treatment Cycle, a vaginal examination with investigator's rating of signs should be completed. Additionally, vulvovaginal samples should be obtained for KOH testing and pH measurements by the local laboratory, fungal culture by the central laboratory and investigation of other pathogens such as bacterial vaginosis and *Trichomonas vaginalis* by the local laboratory.

If the KOH test is negative, the investigator should consider other causes for the persistence or worsening of the symptoms as additional antifungal medication may not be indicated.

If the investigator's rating of the vulvovaginal signs and vaginal sample collection is not possible prior to the initiation of the additional therapy, it should still be completed as soon as possible after additional therapy is initiated.

In addition to the vaginal examination, the symptoms that led to the use of additional antifungal therapy should be documented in the eCRF and the following procedures should also be completed:

- If additional antifungal therapy is administered prior to or at the TOC visit, all TOC visit procedures should be completed, and no additional visits will be needed. The subject will be considered as early termination due to lack of efficacy prior to or at TOC.
- If additional antifungal therapy is administered after the TOC visit but prior to or at the FU visit, all FU visit procedures should be completed, and no additional visits will be needed. The subject will be considered as early termination due to lack of efficacy after TOC but prior to or at FU.

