21. APPENDICES

APPENDIX 1. PROHIBITED MEDICATIONS AND MEDICATIONS TO BE ADMINISTERED WITH CAUTION

Prohibited Medications

The use of any topical vaginal corticoids and topical vaginal contraceptives is prohibited during the study. No systemic or topical vaginal antifungal treatment other than the study drug is allowed during the study unless used as rescue medication after the subject has been documented as not responding to study drug. No investigational drugs other than the study drug are allowed within 30 days before Screening and for the entire duration of the study. In addition, the medications listed below are also prohibited.

Strong CYP3A4/5 inhibitors and CYP3A4/5 inducers

CYP	Strong Inhibitors ^a	Inducers ^a
3A4/5	Ketoconazole Itraconazole	bosentan carbamazepine phenytoin rifampin St. John's wort long-lasting barbiturates efavirenz etravirine

^a. The CYP3A4/5 inhibitors and CYP3A4/5 inducers listed in this table are not permitted during the 7 days prior to enrollment and during study treatment until TOC.

Medications to be administered with Caution and Monitored as Appropriate

CYP3A4 substrates

CYP	Substrates
3A4	
In vitro, ibrexafungerp (SCY-078) was an inhibitor of CYP3A mediated metabolism of midazolam, but was only a weak inhibitor of metabolism of testosterone. The clinical significance of this inhibition is unknown; caution should be exercised when administering ibrexafungerp (SCY-078) with drugs known to be CYP3A sensitive substrates with narrow therapeutic index, such as midazolam and cyclosporine.
 
Subjects receiving sirolimus, tacrolimus, warfarin, cyclosporine or amiodarone are permitted for enrollment in the study and these medications may be administered concomitantly with ibrexafungerp (SCY-078) with close monitoring. Dosing adjustments and subsequent monitoring of sirolimus and warfarin should be undertaken in accordance with product prescribing information for the respective agents.

OATP1B3 substrates

OATP	Substrate

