6.3.2. Eligibility and Protocol Deviations

Eligibility status based upon meeting protocol entrance criteria (ex: resistant/intolerant/prophylaxis failures, etc.) and protocol deviations will be listed by subject. Protocol deviations recorded will be reviewed and major deviations will be identified prior to database lock. The PP population will be determined and subjects with major protocol violations, entry criteria violations or missing visits will be excluded.

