6.3.6. Study Drug Administration

Treatment Cycle 1: All randomized subjects

Subjects who meet all the inclusion and none of the exclusion criteria will be randomized to treatment and stratified into 2 groups based on the Candida species and presence or absence of underlying conditions. Subjects will receive open-label oral ibrexafungerp 300 mg BID for one, three or seven consecutive days per [TABLE 1](#):

| Treatment Group | Criteria | Ibrexafungerp Dose Randomization and Stratification |
|-----------------|---|---|
| Group A | Subjects without underlying medical conditions AND known to have isolates other than C glabrata, C krusei, C auris | 1 Day dosing (300mg AM and 300mg PM) N = 50 |
| Group B | Subjects with underlying medical conditions: DM, immunocompromised conditions (e.g. HIV), debilitation, immunosuppressive therapy (e.g. corticosteroids), recurrent VVC (≥ 3 episodes/year) AND/OR known to have C glabrata, C krusei or C auris isolates | 3 Days or 7 Days dosing (300mg AM and 300mg PM) Randomized 1:1 N = 50:50 |

6.4. Efficacy Analyses Cycle 1

The efficacy analyses will be conducted using the MITT (primary analysis population), ITT and PP populations to evaluate ibrexafungerp. Efficacy outcomes will be presented by treatment group in Cycle 1.

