6.4.1.2. Main Analysis Approach

Clopper-Pearson method will be used to summarize 95% CI of proportion of clinical cure for group A and group B separately. Pairwise treatment comparison of subjects in group B 3 days vs. subjects in group B 7 days will be performed to test primary efficacy endpoint (clinical cure at TOC visit) using a Fisher's Exact

test; p-values and 95% confidence intervals for odds ratio will be presented. The primary endpoint will also be analyzed of subjects in group B 3 days vs. subjects in group B 7 days using a Cochran-Mantel-Haenszel row mean scores test stratified by site.

VSS scores at Baseline, TOC, and FU will be summarized for each sign and symptom using frequency counts and percentages.

Summary statistics will be provided for the total VSS composite score (observed value and change from baseline). Student's t-test will be used for pairwise treatment comparison of subjects in group B 3 days vs. subjects in group B 7 days; p-values and 95% confidence intervals will be presented for the differences between treatment groups.

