6.4.2. Secondary Efficacy Analyses

6.4.2.1. Definition of Secondary Endpoint

The following treatment outcome definitions will be used for the assessment of efficacy relative to baseline: Clinical Outcome.

- Clinical Cure: Complete resolution of signs and symptoms with total composite score of 0 on the VSS Scale and with no additional antifungal therapy required based on investigator's judgment.
- Clinical Improvement: Partial resolution of signs and symptoms with total composite score of 1 or 2 on the VSS Scale and with no additional antifungal therapy required based on investigator's judgement.
- Clinical Success: At least 50% reduction from Baseline in the total composite VSS score with no additional antifungal therapy required based on investigator's judgment .
- Clinical Failure: Persistence and/or worsening of signs and symptoms or need for additional antifungal therapy (this definition also applies to cycle 2 patients).

The following mycological outcome definitions will be used for the assessment of subjects with mycological response.

- Mycological Eradication: Negative culture for growth of *Candida* species .
- Presumed Eradication: Subject is asymptomatic, therefore cultures not done .
- Mycological Persistence: Positive culture for growth of *Candida* species.

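### The Per-Protocol set drops efficacy failures who stop drug on Days 4–7 from the 7-day arm only, tilting the supportive 3- versus 7-day comparison toward 7 days

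*SAP*

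**What the plan says.** SAP 6.2 and Protocol 18.2 build PP from "All MITT subjects who have completed the study drug treatment", and further require no important deviation bearing on efficacy and a TOC evaluation. Neither defines completion or ties it to a day common to both arms. SAP 6.3.2 adds that "subjects with major protocol violations, entry criteria violations or missing visits will be excluded", without saying which visits count.

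Group B is randomised 1:1 to 3 or 7 days, 50 per arm (Protocol 12.1; SAP 6.3.6). SAP 6.4 states: "The efficacy analyses will be conducted using the MITT (primary analysis population), ITT and PP populations". In SAP 6.4.1.2, "Pairwise treatment comparison of subjects in group B 3 days vs. subjects in group B 7 days will be performed" for clinical cure at TOC, by Fisher's exact test and a site-stratified Cochran-Mantel-Haenszel test, with a t-test for the VSS score. SAP 6.4.3.1 names PP for time to resolution, and 6.4.3.2 compares the two Group B arms by log-rank.

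Three provisions govern a subject rescued early. Protocol 11.4: "If additional antifungal therapy is administered prior to or at the TOC visit, all TOC visit procedures should be completed", no later visits are needed, and "The subject will be considered as early termination due to lack of efficacy prior to or at TOC". Protocol Appendix 1 bars other antifungals "unless used as rescue medication after the subject has been documented as not responding to study drug". SAP 6.4.2.1 defines clinical failure as "Persistence and/or worsening of signs and symptoms or need for additional antifungal therapy".

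**The concern.** PP conditions on an event after randomisation, and the window in which that event can occur differs by arm: Days 1–3 in one, Days 1–7 in the other. Through Day 3 the rule acts alike in both arms. From Day 4 to Day 7 only a 7-day subject can still fail to complete. When the reason for stopping is lack of efficacy, the exclusion is tied to the outcome being compared.

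At stake is the reading of the PP result. If PP favours 7 days more than MITT does, a reader may take it as support for the longer regimen among adherent patients, when part of the difference comes from how the set is defined.

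**Working it through.** **No plan figure to reproduce.** The documents give no power, target difference or expected PP size. The allocation adds up: 50 + 50 + 50 = 150.

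**Same course, two arms.** Take a subject whose symptoms persist and who is switched to another antifungal on Day 5 after documented non-response.

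| PP condition | 3-day arm | 7-day arm |
|---|---|---|
| Study drug completed (SAP 6.2) | Yes, on Day 3 | No |
| TOC evaluation (Protocol 11.4) | TOC procedures done | TOC procedures done |
| Rescue a deviation in itself (Appendix 1) | No | No |
| Clinical outcome (SAP 6.4.2.1) | Failure | Failure |
| In PP by SAP 6.2 | Yes, as a failure | No |

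A 7-day subject whose symptoms persist but who takes all her doses has completed treatment and stays in PP as a failure.

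**Inputs for the size.**
- p, true cure rate, equal in both arms: 50.5% and 63.3%, the ibrexafungerp rates in the two placebo-controlled studies in Protocol 7.1.4. Those were 1-day studies in acute VVC, so p is an assumption here.
- d, share of the 7-day arm that stops on Days 4–7 and leaves PP: no document gives it. I use 2%, 5% and 10% as assumptions.

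**Every stopper a failure.** The 3-day PP rate is p and the 7-day PP rate is p/(1 − d).

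| d | p = 50.5% | Shift (points) | p = 63.3% | Shift (points) |
|---|---|---|---|---|
| 2% | 0.505/0.98 = 51.5% | +1.0 | 0.633/0.98 = 64.6% | +1.3 |
| 5% | 0.505/0.95 = 53.2% | +2.7 | 0.633/0.95 = 66.6% | +3.3 |
| 10% | 0.505/0.90 = 56.1% | +5.6 | 0.633/0.90 = 70.3% | +7.0 |

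**Effect on the Fisher test.** Exact binomial enumeration, two-sided 5%, equal true rates, 3-day arm of n against a 7-day arm of n(1 − d), rounded. I use n = 50 as randomised. I also use n = 32, because PP sits inside the culture-positive set: 188 of 298 ibrexafungerp subjects in the second study were in its mITT set, and 50 × 188/298 ≈ 32.

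| n | p | d = 0 | 2% | 5% | 10% |
|---|---|---|---|---|---|
| 50 | 50.5% | 3.5% | 4.5% | 5.0% | 6.8% |
| 50 | 63.3% | 3.1% | 4.0% | 5.3% | 9.6% |
| 32 | 50.5% | 3.3% | 4.4% | 4.5% | 5.6% |
| 32 | 63.3% | 2.9% | 3.9% | 4.4% | 6.2% |

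**Stoppers for an adverse event.** An adverse event is not part of clinical failure, so these subjects may or may not be cured. If they are cured at the same rate as the others, the shift is 0. If all are cured, the 7-day PP rate is (p − d)/(1 − d). At d = 10% that is 0.405/0.90 = 45.0% (−5.5 points) or 0.533/0.90 = 59.2% (−4.1 points). The direction is not fixed.

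**The one documented withdrawal rate.** Protocol 7.1.4 reports 2 of 247 (0.8%) withdrawn from study drug for adverse events with 1-day dosing. Put into the all-failures formula, it gives 0.505/0.992 = 50.9% (+0.4) and 0.633/0.992 = 63.8% (+0.5). It does not bound lack-of-efficacy switching on Days 4–7 in patients who had failed fluconazole.

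**The case against.** The strongest reply is that little rests on PP. MITT is primary; MITT and ITT have no completion rule; the study is exploratory and not powered for comparisons; and requiring completion is conventional. SAP 6.4.1.2 names no population for the Fisher test, so its use in PP comes from the general sentence in SAP 6.4. Discontinuation reasons are tabulated by treatment group anyway. All of this stands and makes the point secondary. It does not remove it: SAP 6.4 puts the efficacy analyses in PP, and SAP 6.4.3.1 does so by name for time to resolution.

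Second, the rescued 3-day subject may not stay in PP. She has no visits after rescue, so the missing-visits wording in SAP 6.3.2 could remove her. It is also unsettled whether procedures done near Day 5 count as the TOC evaluation. Against that, Protocol 11.4 says later visits are not needed, so they are hard to call missing. If she were removed, PP would lose rescued failures from both arms and overstate cure in both. Either reading needs a repair.

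Third, the affected group may be small. Days 3, 5 and 7 are phone contacts, and the first scheduled post-baseline examination is TOC, so a switch on Days 4–7 needs an off-schedule decision. That is fair, and it is why no size can be fixed.

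A reader might also infer that intolerance on Days 4–7 counts as failure in the 3-day arm and so adds to the bias. The documents do not support this. A 3-day subject with an adverse event on Day 5 keeps her own VSS outcome, and excluding 7-day adverse-event stoppers can shift the comparison either way or not at all.

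**Conclusion.** The point holds for efficacy failures who stop study drug or are switched on Days 4–7. The PP definition removes them from the 7-day arm and keeps them as failures in the 3-day arm. With equal true cure of 50.5% to 63.3% and every stopper a failure, the spurious PP advantage for 7 days is about +1.0 to +1.3 points at 2% stopping, +2.7 to +3.3 at 5% and +5.6 to +7.0 at 10%. This rests on assumed stopping rates, on cure rates borrowed from acute VVC, and on the rescued 3-day subject not being excluded for missing visits.

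Two wider conclusions might be drawn and are not supported. One is that the main 3- versus 7-day result is biased; MITT and ITT are unaffected. The other is that the bias is known to be large; no Days 4–7 stopping rate appears in either document. The change is still worth making before database lock, because the exclusion depends on both arm and outcome and is cheap to remove.

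**What to change.** - **SAP 6.2.** Define PP as MITT subjects who completed study drug, or who stopped it early for lack of efficacy or because additional antifungal therapy was started. Retain the latter as failures in both arms. Retain subjects who stopped for an adverse event and have a TOC evaluation with their observed TOC outcome. Making them automatic failures would create the opposite bias: with p = 50.5% and 10% stopping, 7-day cure would become 0.505 × 0.90 = 45.5%, about −5 points. The deviation and TOC-evaluation conditions otherwise stand.
- **SAP 6.3.2.** State that visits not required after early termination for lack of efficacy under Protocol 11.4 are not missing visits. Tabulate PP exclusions by arm and reason.
- **Alternative.** Report PP rates by regimen and do not run the 3- versus 7-day tests in PP.

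The cost is a few SAP sentences and a note that the set departs from Protocol 18.2. No new data are needed. The small downside is that PP then includes some subjects with incomplete dosing.

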6.3. Demographics and Study Summary

6.3.1. Patient Disposition

The number of subjects enrolled, number completing the study, and reasons for discontinuation will be summarized by treatment group and by cycle.

6.3.2. Eligibility and Protocol Deviations

Eligibility status based upon meeting protocol entrance criteria (ex: resistant/intolerant/prophylaxis failures, etc.) and protocol deviations will be listed by subject. Protocol deviations recorded will be reviewed and major deviations will be identified prior to database lock. The PP population will be determined and subjects with major protocol violations, entry criteria violations or missing visits will be excluded.

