15. STUDY SCHEDULE

Detailed schedules of all study visits and procedures are presented in Schedule of Visits and Procedures ([Table 1](#)).

The actual visits will be dependent on the Dosing Group i.e there may be overlapping visits.

Subjects entering Treatment Cycle 2, will follow the same Schedule of Visits and Procedures, starting with Baseline visit and may have visits that are Not Applicable during Treatment Cycle 1.

Table 1: Schedule of Visits and Procedures (Study SCY-078-307b)

Visit	V1 Screening ^a	V2 Baseline ^a	At Home	V3 TOC	V4 FU	V5 FU	V6 FU	V7 FU	Unscheduled Visits ^b
Day (allowable window)	Day -2(±1)	Day 1	Days 2-7	14 ±3 days post Baseline	14 ±3 days post EOT	30±4 days post Baseline	30 ±4 days post EOT	60 ±4 days post EOT	
Study Procedures									
Informed consent	X								
Enrollment and assignment of Subject ID number	X								
Inclusion/exclusion criteria ^c	X	X							
Medical history and demographics	X								
Abbreviated physical exam	X			X					If needed
Vital Signs ^k	X	X		X					If needed
Urine pregnancy test ^c	X			X					If needed
Safety laboratory blood tests ^d	X			X					If needed

Visit	V1 Screening ^a	V2 Baseline ^a	At Home	V3 TOC	V4 FU	V5 FU	V6 FU	V7 FU	Unscheduled Visits ^b
Day (allowable window)	Day -2(±1)	Day 1	Days 2-7	14 ±3 days post Baseline	14 ±3 days post EOT	30±4 days post Baseline	30 ±4 days post EOT	60 ±4 days post EOT	
Rating of vulvovaginal symptoms by the Subject^e	X	X	X	X	X	X	X	X	If needed
Vaginal Examination and rating of vulvovaginal signs by the Investigator^e	X			X	X	If symptoms	If symptoms	If symptoms	If needed
Vulvovaginal sample for other pathogens^e	X			If needed	If needed	if needed	If needed	If needed	If needed
Vulvovaginal sample for KOH and pH^e	X			If symptoms	If symptoms	If symptoms	If symptoms	If symptoms	If needed
Vulvovaginal sample for fungal culture^e	X			X	X	If symptoms	If symptoms	If Symptoms	If needed
Quality of Life Questionnaire		X		X	X	X	X	X	
Study drug dosing		X	X						
Study drug container(s) collection and subject data reviewed				X					
Phone Contact^h			X						
Prior and concomitant medication reviewⁱ	X	X	X	X	X	X	X	X	X
AE monitoring^j	X-----X				X	X	X	X	X

Abbreviations: AE = adverse event; D = day; TOC = test of cure; V = visit; FU = follow up

- a) Screening and Baseline may occur on the same day.
- b) Unscheduled visits can occur if the investigator determines there is a need for one outside of the scheduled per protocol visits.

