6.4.3.3. Additional Estimates

For the subgroup analyses by Candida species, only descriptive statistics will be provided; no statistical testing will be performed due to possible small sample size.

All other efficacy data will be summarized, but not subject to formal statistical analysis.

6.5 Treatment Cycle 2

A second treatment cycle will be allowed for subjects who did not achieve sufficient clinical improvement (e.g. VSS remains ≥ 3) on the randomized treatment (Cycle 1) as evaluated at the TOC and FU visits. A second treatment cycle will also be allowed for subjects with clinical cure/improvement/success who experience a recurrence before the last FU visit. During Cycle 2, subjects may receive additional treatment with ibrexafungerp for a period up to 14 days as recommended by the investigator and following discussion with the sponsor.

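### SAP 6.3.2 excludes subjects with unspecified missing visits from Per-Protocol, contrary to SAP 6.2; applied as written, PP membership would depend on treatment outcome

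*SAP*

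**What the plan says.** The documents describe PP membership in two ways.

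- **SAP 6.2** takes MITT subjects who finished study drug, "who did not have major protocol deviations likely to affect study efficacy AND who have a TOC evaluation". Protocol 18.2 is the same, and the protocol synopsis agrees in substance (data available at TOC). No follow-up visit is required.
- **SAP 6.3.2** says that PP will be determined and that "subjects with major protocol violations, entry criteria violations or missing visits will be excluded". Missing visits stand as a separate ground, and no visit is named.

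Three further provisions decide who has later Cycle 1 visits.

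- **Protocol 11.4, additional antifungal at or before TOC:** "all TOC visit procedures should be completed, and no additional visits will be needed". The protocol adds: "The subject will be considered as early termination due to lack of efficacy prior to or at TOC".
- **Protocol 11.4, additional antifungal after TOC:** "all FU visit procedures should be completed, and no additional visits will be needed".
- **Protocol 15:** subjects entering Cycle 2 follow the same schedule again, "starting with Baseline visit and may have visits that are Not Applicable during Treatment Cycle 1". SAP 6.5 opens Cycle 2 both to subjects without sufficient improvement and to subjects with cure, improvement or success who then recur.

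SAP 6.4 names MITT as primary and runs the efficacy analyses on ITT and PP as well.

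**The concern.** A PP population should select on adherence to the protocol, not on how the subject fared. Under 6.2, a subject who finished study drug, had her TOC assessment and was then rescued for lack of efficacy stays in PP as a failure. Under 6.3.2 read literally, she can be removed because the visits after TOC were not done, and they were not done because treatment failed. A non-responder whose Cycle 1 follow-up is replaced by Cycle 2 is in the same position. So is a subject cured at TOC who recurs and is rescued or re-dosed.

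A PP cure rate that differs from MITT would normally be read as the effect in compliant subjects. Here the difference could come from events after TOC. The study is open-label and the SAP does not define a missing visit, so membership would rest on interpretation at the deviation review before database lock.

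**Working it through.** **Plan's own figure.** There is none to reproduce. The documents give no PP rate, no expected cure rate for this trial, and no rate of rescue or Cycle 2 entry. The shares below are assumptions shown as a range.

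**Step 1. Who is treated differently by the two rules?** Each row assumes study drug completed, no major deviation and a TOC evaluation present.

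| Subject | SAP 6.2 | SAP 6.3.2, any visit |
|---|---|---|
| Rescued at TOC for lack of efficacy | in, as failure | could be out |
| Not improved at TOC, enters Cycle 2 | in, as failure | could be out |
| Cured at TOC, recurs, rescued or re-dosed | in, as cure at TOC | could be out |
| VSS 1 or 2 at TOC, no further therapy needed | in, as non-cure | normally in |
| Cured at TOC, no recurrence | in, as cure | in if all visits are counted as done |

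The first three rows differ only because of the subject's course after treatment.

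**Step 2. Effect on the TOC cure rate.** Let p be the MITT cure rate at TOC, f the share of non-cures removed and g the share of TOC cures removed.

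PP rate = p(1−g) / [p(1−g) + (1−p)(1−f)]

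Equivalently, PP odds = MITT odds × (1−g)/(1−f). The rate rises if f > g, is unchanged if f = g and falls if f < g.

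**Step 3. Numbers.** Take p = 50% (assumed) and, for intervals, 50 MITT subjects with 25 cures. Fifty is the planned size per treatment duration; the MITT count may be smaller. Intervals are Clopper-Pearson, as in SAP 6.4.1.2.

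| f | g | Calculation | PP rate | 95% CI |
|---|---|---|---|---|
| 0 | 0 | 25/50 | 50.0% | 35.5–64.5 |
| 20% | 0 | 25/45 | 55.6% | 40.0–70.4 |
| 40% | 0 | 25/40 | 62.5% | 45.8–77.3 |
| 60% | 0 | 25/35 | 71.4% | 53.7–85.4 |
| 40% | 20% | 20/35 | 57.1% | 39.4–73.7 |
| 40% | 40% | 15/30 | 50.0% | 31.3–68.7 |
| 20% | 40% | 15/35 | 42.9% | 26.3–60.6 |

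The first row is also the result under the 6.2 definition, where rescue or re-dosing alone removes nobody who has a TOC evaluation.

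**Step 4. Group B, 3 versus 7 days.** Assume cure rates of 40% and 60%, with f = 60% and g = 0 in both arms.

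- 3 days: 0.40/(0.40 + 0.60×0.4) = 62.5%.
- 7 days: 0.60/(0.60 + 0.40×0.4) = 78.9%.
- The difference falls from 20.0 to 16.4 points. The odds ratio, the effect measure in SAP 6.4.1.2, stays at 2.25 because both odds are multiplied by the same factor. It would move only if (1−g)/(1−f) differed between arms.

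**Step 5. Coinciding visits.** Protocol 15 allows for overlapping visits. With one-day dosing, end of treatment falls on Day 1, so the two 14-day visits fall together, as do the two 30-day visits. If a merged visit left one of the pair recorded as not done, an any-visit rule could flag fully compliant Group A subjects.

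**The case against.** The strongest reply is that a visit the protocol waives is not missing. Protocol 11.4 says further visits are not needed after rescue, and section 15 calls some Cycle 1 visits not applicable. Early termination under 11.4 follows the protocol and is no deviation. PP is defined in SAP 6.2 and protocol 18.2, and 6.3.2 can be read as shorthand for a missing TOC evaluation. The any-visit reading is also awkward in itself, since it could exclude compliant Group A subjects. This is a sensible reading and may be the intended one, but the SAP does not state it: 6.3.2 lists missing visits as their own ground and exempts nothing.

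A reader might go further and infer that PP loses failures by design and so overstates cure. The documents do not support that:

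- It requires counting waived visits as missing.
- Subjects cured at TOC who recur can leave by the same two routes, so the TOC rate can move either way.
- Not all non-cures leave. Those with VSS 1 or 2 and no need for further therapy would normally stay on schedule, and Cycle 2 is permitted, not required.
- Some rescued subjects are outside PP under 6.2 anyway, for instance if they did not finish study drug.

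Nor does the rule necessarily inflate the 3- versus 7-day comparison, as step 4 shows.

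The reply that the consequence is limited also stands in part. MITT is primary, the study is exploratory and not powered for formal comparisons, and PP is supportive.

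**Conclusion.** SAP 6.2 and 6.3.2 give different PP populations. Under the literal wording of 6.3.2, membership depends on events after TOC that are driven by treatment outcome. This is established from the text. Whether the rule would be applied that way is not.

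If it were, the shift could be material: from an assumed 50%, the examples run from 42.9% to 71.4%. The size and sign rest entirely on the assumed shares leaving, for which the documents give no figures. What can be said without them is that the PP rate at TOC moves up, not at all, or down as the share of non-cures leaving exceeds, equals or falls short of the share of cures leaving. The primary MITT analysis is untouched. The point should be settled before database lock, but it does not threaten the main result.

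**What to change.** In SAP 6.3.2, strike the missing-visits ground, or replace it with a missing TOC evaluation, so that it matches 6.2 and protocol 18.2. Then add a sentence along these lines:

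*Visits not done because of early termination for lack of efficacy, entry into Cycle 2, or coinciding visit dates are not a reason for exclusion from PP. Subjects otherwise meeting the 6.2 definition are kept with their observed TOC outcome and are counted as failures at later visits where they met the failure definition.*

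The cost is SAP wording only, with no change to data collection or conduct. The downside for the sponsor is that the PP cure rate may be less favourable than under the literal rule.
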